5.3.1 Discontinuation of study drug

The Investigator or designee may discontinue dosing in a patient if the patient:

- Is in significant violation of the protocol
- Is non-adherent to treatment regimen
- Experiences a serious or intolerable AE, a life-threatening bleeding episode, eg, any gastrointestinal hemorrhage or intracranial hemorrhage, or life-threatening thromboembolic event
- Requires a prohibited medication
- More than 1 AT measurement <15% if at a dose of 50 mg Q2M

The Investigator will confer with the Sponsor or study Medical Monitor before discontinuing dosing in the patient.

Patients (or their guardians) may decide to discontinue study drug.

In general, patients who discontinue study drug dosing for any reason will be encouraged to remain on the study to complete the remaining assessments through the end of study so that their experiences are captured in the final analyses. If a patient discontinues dosing due to a serious adverse event (SAE), the SAE should be followed as described in [Section 7.6.6](#). When a patient discontinues study drug dosing, the primary reason must be recorded in the appropriate section of the eCRF. Patients who discontinue study drug but who remain on study may receive treatment consistent with local standard practice for their disease per Investigator judgement, as applicable. Safety will be captured for the entire duration of study for patients who discontinue treatment.

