6.3.2.2 Bleeding episode management recommendations for patients during the fitusiran treatment period (for the United States specific requirements, see Appendix 11.5.1.2)

Given the mechanism of action and pharmacodynamics profile of fitusiran, the factor or BPA dose necessary to safely and effectively treat breakthrough bleeding episodes in patients receiving fitusiran during the fitusiran treatment period will be lower than standardly prescribed. This is supported by data from the Phase 1 study in which bleed events were managed with factor or BPA, as well as additional modeling and ex vivo spiking data. More detailed information on the clinical experience in bleeding episode management in Phase 1 and Phase 1/2 fitusiran studies, as well as supportive nonclinical studies is provided in the Investigator's Brochure.

After administration of fitusiran, AT lowering will be progressing toward therapeutic levels. As quickly as 7 days after the initial fitusiran dose, the majority of patients will have AT levels at or below 60% residual activity. By 14 days after dosing, it is expected that 94% of patients will have AT lowering of >50%, with a median value of 66.8%. Based on these AT kinetics, it is recommended that patients continue with their standard factor or BPA regimens for the first 7 days following initiation of fitusiran dosing, with institution of the protocol-specific bleed management guidelines with reduced factor or BPA at Day 8 and beyond ([Table 6](#)).

Patients on fitusiran will be provided a written bleed management plan with appropriate dosing of factor or BPA for use during Day 1 through 7, as well as a bleed management plan with dosing for Day 8 and beyond. Thereafter the bleed management plan will be reviewed and updated at monthly visits, and new written plans provided to the patient if dosing changes.

Importantly, after Day 7 of the fitusiran treatment period, patients should not use factor, BPA, or other hemostatic agents as prophylaxis for bleeding episode prevention, including doses related to anticipated hemostatic challenges such as physical activity. For prophylaxis of bleeding episodes in patients who require operative procedures see [Section 6.6](#).

Bleed Management Guidelines Day 1 to Day 7 of Fitusiran Treatment Period:

Patients should be instructed to call the site prior to administering factor or BPA for the management of bleeding episodes. Patients should continue with their standard factor or BPA regimens.

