8.2.5.1 Primary endpoint

The primary analysis will be performed on the EAS and will include all bleeding episodes occurring in the factor or BPA prophylaxis period (Day -162 to Day -1) and the fitusiran efficacy period (Day 29 to Day 190). If a patient does not have bleeding episode data collected after Day 28 (eg, due to early study discontinuation), the available bleeding episode data starting from Day 1 will be used in the primary analysis. To avoid confounding the treatment effect, bleeding episode data during and after major surgery, antithrombin administration, major trauma, or initiation of prophylaxis treatment with factors or BPAs during the fitusiran treatment period will be excluded from the primary analysis.

The number of bleeding episodes will be analyzed using a repeated measures negative binomial model with fixed effect of treatment period. The logarithm number of days that each patient spends in the efficacy period matching the bleeding episode data being analyzed will be included as an offset variable to account for unequal follow-up time due to early withdrawal or surgery. The ratio of bleeding rates in the fitusiran efficacy period to the factor or BPA prophylaxis period and its 95% CI and p-value will be presented. The p-value should be interpreted with caution. In addition, as a contrast Bayesian analyses will be performed to summarize the point estimates of the posterior probability of a clinically significant treatment effect, along with associated measures of uncertainty. The estimated mean ABRs in these 2 periods along with their 95% CIs will be presented from this model. In addition, summary statistics for ABR, including the median and interquartile range, will be presented for each treatment arm, where ABR is defined as:

$$\frac{\text{total number of qualifying bleeding episodes}}{\text{total number of days in the respective period}} \times 365.25$$

Patients who discontinue treatment during the study will be strongly encouraged to continue recording bleeding episode data.

For the United States specific requirements, see [Section 11.6.1.2](#).

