		To clarify the analysis of the annualized weight-adjusted consumption of factor/BPA	The parameters to be summarized for the consumption of factor/BPA is modified to: annualized weight-adjusted factor/BPA consumption for both treating bleeds and prophylaxis purpose, number of factor/BPA injections per bleed/per subject, weight adjusted total dose per bleed/per subject. The summary of compliance to the bleed management guideline is added.
		To add the AE summary related to Covid-19 infection	AE potentially consistent with COVID-19 will be summarized by SOC and PT and list will also be provided. The search term list is added in the Appendix G.
		To add AE summary by hemophilia type	By hemophilia type summary is added to key AE tables.
		Due to the exclusion criteria 5, the analysis of fibroscan/fibrotest result at baseline against worst post-baseline ALT elevation is not necessary	The related analysis is removed in Section 2.4.5.2.
		Appendix A Potentially clinically significant abnormalities criteria is not applicable to this study	Appendix A Potentially clinically significant abnormalities criteria is removed
3	This version	Removed 80mg for fitusiran dosing and fitusiran prophylaxis period	To accommodate the new dose regimen of 50mg Q2M per protocol V6.0.
		Added safety analysis set 1, safety analysis set 2, efficacy analysis set 1, and efficacy analysis set 2	To accommodate the new dose regimen of 50mg Q2M per protocol V6.0.
		Removed pharmacokinetics analysis set	No PK analysis planned in this SAP

SAP version number	Date approved	Rationale	Description of statistical changes
		Added one more major pd which will lead to PPS exclusion: The participant did not administer prophylaxis therapy with minimum frequency as per protocol (table 5) during the prophylaxis period	To exclude patient with poor compliance during prophylaxis period.
		Clarified Covid-19 Unaffected Set is a subset of EAS 1	To add clarification.
		Updated the intercurrent event of fitusiran treatment discontinuation	To accommodate the new dose regimen of 50mg Q2M per protocol V6.0.
		Updated the intercurrent event of prophylaxis treatment	Prophylaxis BPA and Factor are prohibited.
		Added AESI of Cholecystitis and Cholelithiasis	Added AESI per protocol V6.0.
		Clarified the patients with 80mg QM and participants with 50mg Q2M will be analyzed separately and relevant scope	To accommodate the new dose regimen of 50mg Q2M per protocol V6.0.

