The factor/BPA prophylaxis period, fitusiran onset period, efficacy period and treatment period also exclude the period of following intercurrent events to avoid confounding of treatment effect for the primary efficacy analysis based on On-Treatment Strategy.

- Permanent fitusiran treatment discontinuation during treatment period: Exclude events occurring on any dates starting from the date of the last dose within treatment period +29 days. For patients whose last dose is on 50 mg/20 mg Q2M regimen, the “29 days” adjustment will be replaced with 57 days.
- Perioperative period of major surgery. The perioperative period is defined as the day of the surgery through the final day on which supplemental hemostatic or antithrombotic treatments are administered as part of the perioperative treatment plan.
- Period of minor surgery is defined as the perioperative period of surgery above or to 72 hours from the end of surgery, whichever is later.
- Period of antithrombin treatment is defined as the first day of antithrombin treatment through the final day on which antithrombin or other anticoagulant therapies are administered plus 5 half-lives of that specific product.
- After prophylactic treatment with emicizumab.

The summary statistics for number of patients who are lost-to-follow-up and who had each intercurrent event will be provided.

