Inhibitor, as evidenced by:

- Use of bypassing agents for prophylaxis and for any bleeding episodes for at least the last 6 months prior to Screening,
- Meeting one of the following Nijmegen-modified Bethesda assay results criteria:
 - Inhibitor titer of ≥ 0.6 BU/mL at Screening, or
 - Inhibitor titer of <0.6 BU/mL at Screening with medical record evidence of 2 consecutive titers ≥ 0.6 BU/mL, or
 - Inhibitor titer of <0.6 BU/mL at Screening with medical record evidence of anamnestic response,

- The subgroup of patients in Cohort A patients must additionally meet the following criteria to be eligible to start treatment with fitusiran directly after the screening period:
 - Hemophilia B with inhibitory antibody to FIX as defined above and
 - Not responding adequately to BPA treatment (historical ABR ≥ 20) prior to enrollment and
 - In the opinion of the Investigator, with approval of sponsor medical monitor, 6-month BPA prophylaxis period should be omitted.

Non-inhibitor, as evidenced by:

- Use of factor concentrates for prophylaxis and for any bleeding episodes for at least the last 6 months prior to Screening,
- Meeting each of the following criteria:
 - Nijmegen-modified Bethesda assay inhibitor titer of < 0.6 BU/mL at Screening and
 - No use of bypassing agents to treat bleeding episodes for at least the last 6 months prior to Screening and
 - No history of immune tolerance induction therapy (ITI) within the past 3 years prior to Screening,
- The participant did not receive prescribed prophylactic treatment of hemophilia with factor concentrates or bypassing agents for at least 6 months prior to Screening, or did not receive a prophylactic regimen consistent with the approved prescribing information for the product or local recommendations, allowing for adjustment to individual patient response, and designed to decrease spontaneous bleeding, but the participant was enrolled.
- The participant has known co-existing bleeding disorders other than hemophilia A or B, but the participant was enrolled
- The participant discontinued prophylactic treatment or withdrew consent during the factor/bypassing agent prophylaxis period, but participant was not withdrawn from the study.
- The participant continued or reinitiated use of factor concentrates or bypassing agents as prophylaxis for bleeding episode prevention, during the fitusiran prophylaxis treatment period but the study drug was not discontinued.

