2.4.4.1 Analysis of primary efficacy endpoint(s)

2.4.4.1.1 Primary efficacy analysis based on on-treatment strategy

The primary objective of this study is to characterize the frequency of bleeding episodes while receiving fitusiran treatment, relative to the frequency of bleeding episodes while receiving factor/BPA prophylaxis. Including bleeding events in the period of intercurrent events such as use of prophylactic medication during fitusiran treatment period or surgery or after fitusiran treatment discontinuation could significantly bias fitusiran effect and make the comparisons difficult to interpret. The on-treatment strategy is considered of greatest relevance in assessing this primary objective (ICH E9 (R1), 2018 (1)).

Global protocol

The number of bleeding episodes is annualized for each patient using the following formula:

$$\text{Annualized bleeding rate (ABR)} = \frac{\text{total number of qualifying bleeding episodes}}{\text{total number of days in the respective period}} \times 365.25$$

The primary analysis includes all bleeding episodes occurring in the factor/BPA prophylaxis period and the fitusiran efficacy period.

Let λ_F represent the ABR during fitusiran efficacy period and λ_O represent the ABR during factor/BPA prophylaxis period. The null and alternative hypotheses of the primary analysis, respectively, can be written as follows:

$$H_0: \frac{\lambda_F}{\lambda_O} = 1 \quad H_A: \frac{\lambda_F}{\lambda_O} \neq 1$$

An estimated ABR ratio $\lambda_F/\lambda_O < 1$ and two-sided p-value < 0.05 from the significance test lead to the rejection of H_0 in favor of H_A ; it is concluded that prophylactic use of fitusiran reduces the frequency of bleeding episodes compared to the factor/BPA prophylaxis therapy.

The ABR ratio λ_F/λ_O is estimated using a repeated measures negative binomial model:

$$\log(\text{number of bleeding episode}) = \beta_0 + \beta_1 \cdot \text{study period} + \log(\text{duration})$$

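### The SAP's on-treatment exclusions name emicizumab prophylaxis but omit factor or bypassing-agent prophylaxis taken during fitusiran, which Protocol 8.2.5.1 excludes from the primary analysis

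*SAP*

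**What the plan says.** SAP 2.1.3.1 removes five kinds of time from the study periods for the primary analysis: time after permanent fitusiran discontinuation (from last dose +29 days on the monthly regimen), major surgery, minor surgery, antithrombin treatment, and "After prophylactic treatment with emicizumab". Factor and BPA prophylaxis are not listed.

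Protocol 8.2.5.1 gives a different list. It says that bleed data during and after "initiation of prophylaxis treatment with factors or BPAs during the fitusiran treatment period will be excluded from the primary analysis". The US version in Protocol 11.6.1.2 has the same rule. Both synopses (global, and US in 11.6.1.1) are narrower: they exclude only data after prophylaxis is re-initiated following fitusiran discontinuation.

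SAP 2.4.4.1.1 justifies the on-treatment strategy this way: "Including bleeding events in the period of intercurrent events such as use of prophylactic medication during fitusiran treatment period or surgery" could bias the fitusiran effect. SAP 1.6, Table 4, version 3 records an update to the prophylaxis event, with the reason "Prophylaxis BPA and Factor are prohibited". It does not say what was taken out.

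**The concern.** A prohibition does not stop an event from happening, and the documents expect this one. Protocol 6.3.2.2 says that "after Day 7 of the fitusiran treatment period, patients should not use factor, BPA, or other hemostatic agents as prophylaxis for bleeding episode prevention". Protocol 5.3.1 includes need for a prohibited medication among its grounds for stopping, but that list opens with "The Investigator or designee may discontinue dosing in a patient if the patient", so stopping is optional. SAP 2.3 then describes a per-protocol deviation in which fitusiran dosing carries on: "The participant continued or reinitiated use of factor concentrates or bypassing agents as prophylaxis for bleeding episode prevention".

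That deviation removes a patient from the per-protocol set, not from Efficacy Analysis Set 1 (EAS 1), on which the primary analysis runs. Time on fitusiran plus regular factor or BPA prophylaxis is therefore analysed as fitusiran time. For this one event the analysis labelled on-treatment behaves like a treatment-policy analysis, contrary to Protocol 8.2.5.1 and to the SAP's own rationale. Two programmers, one following the protocol and one the SAP, would build different primary datasets.

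**Working it through.** **1. The passages side by side**

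| Place | Factor/BPA prophylaxis while still on fitusiran | Restart after fitusiran is stopped |
|---|---|---|
| Protocol 8.2.5.1, global and US | excluded from its start | excluded from its start |
| Both protocol synopses | not mentioned | excluded |
| SAP 2.1.3.1 | retained | excluded from last dose +29 days |
| SAP 2.4.4.1.1 | prophylactic medication called potentially biasing | time after discontinuation called potentially biasing |

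The main gap is use while still on fitusiran. A smaller gap is a restart soon after stopping, which Protocol 6.3.2.3 allows for strong medical need. It is at most about 28 days per patient before the +29-day rule applies. The every-2-months regimen has only 2 participants, whose data are mainly listed (SAP 2.4).

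**2. Whether another analysis replaces the rule**

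- The per-protocol repeat drops whole patients, not the affected time.
- The treatment-policy analysis (SAP 2.4.4.1.2) excludes only surgery-related events.
- The deviation, concomitant-medication and consumption tables describe the use but do not change the estimate.
- SAP 2.1.3.1 promises a count for each intercurrent event. This one is unlisted, so it is not counted.

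**3. Illustrative size**

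The documents give no rate of such use and no figure to reproduce. Inputs:

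- Efficacy window: Day 29 to Day 190, 190 − 29 + 1 = 162 days.
- Cohort A: 30 planned, less up to 4 direct-entry patients outside the efficacy set, n = 26. Cohort B: n = 50.
- Fitusiran ABR as analysed under the SAP: 4 (planning mean, SAP 1.3).
- Assumed: q = 1 or 2 users, d = 81 days each (half the window), bleeding at a = 2 or 6 per year in that time.

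ABR under the protocol rule, by simple pooling = (4 × n × 162 − q × d × a) / (n × 162 − q × d). Difference = 4 / that value − 1.

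Cohort A has 26 × 162 = 4,212 patient-days, and 4 × 4,212 = 16,848.

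- q = 1, a = 2: (16,848 − 162) / (4,212 − 81) = 4.039; the SAP value is 0.97% lower.
- q = 1, a = 6: (16,848 − 486) / 4,131 = 3.961; 0.99% higher.
- q = 2, a = 2: (16,848 − 324) / 4,050 = 4.080; 1.96% lower.
- q = 2, a = 6: (16,848 − 972) / 4,050 = 3.920; 2.04% higher.

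The affected share of person-time is 81 / 4,212 = 1.9% or 162 / 4,212 = 3.8%. Against a BPA-period ABR of 16, the ratio is 4 / 16 = 0.250 under the SAP and 3.920 / 16 = 0.245 to 4.080 / 16 = 0.255 under the protocol rule. The planned interval for that scenario at correlation 0.50 is 0.15 to 0.39.

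Other cases, same formula:

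- Cohort B, 81 days: about ±0.5% (one user) or ±1.0% (two).
- Cohort A, smaller gap, d = 28: about ±0.3% or ±0.7%.
- Cohort A, use on all 162 days: about ±2% (one user); −4.0% to +4.3% (two).

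**4. Two smaller differences from Protocol 8.2.5.1**

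The SAP list lacks the protocol's exclusion for major trauma, a term that neither document defines. The control window runs from Day -168 (168 days) instead of Day -162 (162 days); at a constant bleed rate this leaves the ratio unchanged. Table 4 names neither change.

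**The case against.** The best defence is that the change was deliberate. Table 4 logs it with a reason, and the SAP comes close to the synopsis wording, because the discontinuation rule removes most time after a restart. Use on fitusiran is a protocol deviation, a ground for stopping study drug, a per-protocol criterion, and visible in descriptive tables. Factor given for a procedure or alongside antithrombin largely falls under the surgery and antithrombin exclusions. All of this is fair. A reader might infer that the event was simply forgotten, and the log does not support that. What remains is a thin justification, an event that the SAP itself foresees, and four places that disagree.

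A reader might also infer a bias in fitusiran's favour of up to about 6%. Weighting patients as a negative binomial model would (dispersion 1.69, from ABR mean 4 and SD 6 over 162 days) gives −6.3% when 2 of 26 patients go from 12 bleeds per year to 2. That is one corner of the assumptions, and it mixes two effects: truncated records with high rates gain weight per day. With two patients going from 8 to 6, pooling gives +2.0% and weighting −0.4%. The documents therefore support neither that size nor a fixed direction.

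Finally, exclusion can itself be informative. Protocol 6.3.2.3 gives more frequent bleeding as an example of a reason for early restart, so the excluded time may come from patients doing poorly. This stands, and it is why the current rule should be kept alongside.

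**Conclusion.** The rule in SAP 2.1.3.1 is wrong as written. It keeps in the primary analysis time that Protocol 8.2.5.1 excludes and that falls within what SAP 2.4.4.1.1 calls potentially biasing. The protocol adds to the problem because its synopses and body disagree.

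The likely effect is small: about 1% to 2% of the fitusiran ABR in Cohort A in either direction, assuming 1 or 2 users for 81 days and simple pooling. The true frequency, and hence the true size and sign, cannot be known from the documents. They do not support reading this as a threat to the trial's conclusion. The case rests on pre-specification: the direction depends on who takes prophylaxis, so the rule should be settled before the data are analysed.

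**What to change.** 1. Add to SAP 2.1.3.1 an intercurrent event: regular factor or BPA prophylaxis started or continued after Day 7 of the fitusiran treatment period. Exclude time and bleeds from its start, as Protocol 8.2.5.1 does.
2. Identify it from eDiary doses with reason 'prophylaxis', judged against the product-specific frequencies in Protocol Table 5. A single 14-day gap would fit only extended half-life FIX and could discard valid follow-up in other patients. Confirm cases by data review before database lock. Do not count pre-procedure doses, single doses for activity, or the prescribed Day 1 to 7 overlap.
3. State that the fallback to Day 1 (Protocol 8.2.5.1; SAP 2.1.3.1 and 2.4.4.1.1) applies only to patients without data after Day 28 because of early study discontinuation, not to patients whose efficacy days are all removed by this exclusion. State how the US analysis, which starts on Day 1, treats a patient left with Days 1 to 7 only.
4. Report the number of patients with the event, and keep the current SAP rule as a sensitivity analysis.
5. Align Protocol 8.2.5.1 (global and US), both synopses, SAP 2.1.3.1 and SAP 2.4.4.1.1.
6. Minor: restore the major-trauma exclusion with a definition, or log its removal; log the move of the control window from Day -162 to Day -168.

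The cost is wording and some programming. The eDiary already records a reason for each dose, but its listed reasons include no procedure category, so doses marked 'prophylaxis' need checking against procedure records. A little person-time is lost.

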2.1.3.2 Secondary efficacy endpoints

	Global protocol	US protocol
Key secondary endpoint		ABR in the fitusiran efficacy period
Secondary endpoints	ABR in the treatment period	
	Annualized spontaneous bleeding rate in the fitusiran efficacy period and the factor/BPA prophylaxis period	Annualized spontaneous bleeding rate in the fitusiran efficacy period and the BPA prophylaxis period
	Annualized joint bleeding rate in the fitusiran efficacy period and the factor/BPA prophylaxis period	Annualized joint bleeding rate in the fitusiran efficacy period and the BPA prophylaxis period
	Change in Haem-A-QOL physical health score and total score in the fitusiran treatment period and the factor or BPA prophylaxis period	Change in Haem-A-QOL physical health score and total score in the fitusiran treatment period
	ABR in the onset period	ABR in the onset period
	Annualized weight-adjusted consumption of factor/BPA	Annualized weight-adjusted consumption of BPA

